The Effect of Chronic Antidepressants on PDE4 Binding Building on this work, we sought to determine if antidepressant treatment upregulates PDE4 in humans as it does in animals. In addition to the rolipram PET scans without medication reported above, 22 of the 43 unmedicated MDD patients had a follow up rolipram scan after starting treatment with SSRIs. In this ongoing study, our pre-determined sample size is 25 patients to be scanned after SSRI treatment. These patients showed an increase of 13 \pm 36% in rolipram binding after SSRI treatment across all brain regions (p = 0.001 when age was used as a covariate). In contrast, 11 healthy controls who had a repeat scan without SSRI showed similar binding on repeat scans with changes of only $-2 \pm 13\%$. The change in rolipram binding after SSRI varied markedly among patients as indicated by the large standard deviation of 36%. Those patients with lower rolipram binding before SSRI showed significantly greater increases after therapy (p < 0.007 in all regions) indicating normalization of rolipram binding by treatment. Older patients also showed greater increases in rolipram binding after SSRI ($p \le 0.001$) while young patients with higher baseline rolipram binding tended to show decreased rolipram binding after SSRI. According to the interim analysis, the changes in rolipram binding did not correlate with

Fig 4. $[^{11}C](R)$ -rolipram binding was globally decreased by 18% in brains of unmedicated MDD patients during a major depressive episode (n = 43) compared to matched controls (n = 35; p < 0.001). These mean parametric images of the two groups represent the "absolute" quantitation of radioligand binding calculated on an individual voxel level and using the concentration of radioligand in serial arterial blood samples.

symptom improvement in all patients. Nevertheless, posthoc analyses after the full sample size has been accrued (i.e., 25 patients) may show correlations in subgroups of patients and/or specific regions of brain.

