This study will have two populations: subjects with MAS and healthy control subjects. MAS subjects will be recruited from participants in 98-D-0145 "Screening and Natural History of Patients with Polyostotic Fibrous Dysplasia and the McCune-Albright

Syndrome" (PI: [name]). Participation in our protocol will not delay or interfere with the patient's treatment. For all patients, the diagnosis of MAS will have been made under 98-D-0145.

Healthy subjects will be recruited and screened by the Molecular Imaging Branch (MIB) under a separate protocol (01-M-0254 or 17-M-0181), and group-matched for age to the MAS subjects.

Our accrual number will be 20 for subjects with MAS and 15 for healthy controls. Assuming a withdrawal / dropout rate of \sim 20%, our target is to complete the study with 16 MAS subjects and 12 healthy controls. Both MAS and healthy subjects have one or two PET scans: one whole body and one brain scan. We expect that healthy subjects are more likely to have both brain and whole body scans and MAS subjects are less likely to do so. We expect \sim 10 brain and \sim 10 whole body scan to be performed in each group.

b. Inclusion criteria

Subjects with MAS

- **1.** At least 18 years of age
- 2. Able to provide self-consent
- 3. Diagnosed with MAS under 98-D-0145.
- 4. Have craniofacial fibrous dysplasia

Healthy Subjects

- 1. At least 18 years of age.
- 2. Healthy based on medical history and physical examination.

c. Exclusion criteria

Subjects with MAS

- 1. Serious medical conditions, which may interfere with study procedures. Such conditions include but not limited to significant bone abnormalities in wrist areas of both arms, which makes it difficult to place a radial arterial line, clinically marked dysfunction of liver or kidney, which may delay clearance of $[^{11}C](R)$ -rolipram.
- **2.** Clinically significant laboratory abnormalities not linked to endocrine abnormalities but that may interfere with the PET measurement or affect safety of the participant during this study.
- **3.** Positive HIV test.
- **4.** Head trauma resulting in a period of unconsciousness lasting longer than one hour.
- 5. Metallic foreign bodies that would be affected by the magnetic resonance imaging (MRI) magnet, or fear of enclosed spaces likely to make the subject unable to undergo an MRI scan.
- **6.** Recent research-related exposure to radiation (i.e., PET from other research) that, when combined with this study, would be above the allowable limits.

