The third outcome measure will be the difference in SUV between the baseline and the blocked whole-body scans. SUV is calculated as stated above.

10. Statistical Analysis

a. Analysis of data/ study outcomes

PET and MRI images will be co-registered for anatomic definition of brain regions. Brain and plasma data will be analyzed with compartmental and graphical modeling to calculate $V_{\rm T}$, which is proportional to the density of receptor or enzyme. $V_{\rm T}$ will be calculated both for regions of the brain and on a voxel basis. PET whole body images will be analyzed by drawing organs and by calculating AUC of SUV. For comparisons between subjects with MAS and healthy controls in brain and peripheral organs, an unpaired test, such as t- and Mann-Whitney tests will be used. In addition, in peripheral organs of MAS, for comparisons of PET data between affected and unaffected organs, a paired test will be applied if the contralateral side is unaffected. If contralateral side is also affected or not available, an unpaired test will be applied to compare the same tissue/organ between patients and healthy controls. For the statistical analyses, SPSS, PMOD, SPM, Freesurfer or equivalent programs will be used.

b. Power analysis

This is an exploratory study focusing on PET imaging. Clinical data obtained under 98-D-0145 may be used to interpret the relationship between PET findings and clinical manifestations of the disease. Although constitutive activation of $G_s\alpha$ is expected to increase cAMP signaling, which increases PDE4 levels, PDE4 levels in MAS are not known in postmortem tissue either in brain or in peripheral organs such as bone. Therefore, we cannot do a realistic power calculation.

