To achieve the goals of this exploratory study, we request a total of 35 subjects: ~10 MAS subjects to undergo brain PET scan, ~10 MAS subjects to undergo whole body PET, and 15 healthy controls to undergo a brain scan and/or a whole body PET scan. By limiting subjects with MAS to those who have craniofacial fibrous dysplasia and neuropsychological symptoms, we expect to increase the likelihood of detecting changes in PET in this small sample size. To limit the number of study participants, all MAS and healthy subjects will be asked if they would be willing to have both brain and whole body PET scans. A smaller number of 15 healthy subjects are requested because healthy subjects are more likely to have both brain and whole body scans. Our previous study of [¹¹C](*R*)-rolipram brain scans in healthy subjects found that the coefficient of variation (SD/mean) of VT was 19%. Based on the activation of G_sa, we hypothesize that MAS patients will show increased rolipram binding for whichever one-sided test is appropriate. Assuming a 20% dropout from 10 subjects (thus, eight subjects per group) plus a 19% coefficient of variation (SD/mean) will provide a power of 0.80 to detect a 19% increase.

11. Human Subjects Protection

a. Subject selection

The study will be open to all racial and ethnic groups and will not target any particular group. Healthy volunteers will be recruited to match the patient group for age. Those who are HIV positive are excluded because the possible viral effects on the brain could interfere with interpretation of the outcome of the study.

b. Justification for exclusion of children

We will exclude children younger than 18 years of age to avoid radiation exposure to minors because the risks of radiation exposure outweighs the benefits.

c. Justification for inclusion of other vulnerable subjects

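### Controls are group-matched on age, but the primary brain V_T comparison ignores age; adjusting would gain about 8 to 9 power points if age and V_T correlate at 0.5, little at 0.3, and nothing at 0

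*Combined protocol and SAP*

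**What the plan says.** Section 10a (Analysis of data/ study outcomes) gives the whole between-group analysis in one sentence: for MAS against healthy controls, in brain and in peripheral organs, "an unpaired test, such as t- and Mann-Whitney tests will be used". No covariate is named anywhere in section 10.

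Section 3a says that healthy subjects will be "group-matched for age to the MAS subjects". Section 11a repeats the matching on age, and the Précis adds gender. Both groups are adults with no upper age limit (section 3b).

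The Introduction, under the effect of chronic antidepressants, reports an earlier rolipram result as "p = 0.001 when age was used as a covariate" and remarks that "young patients with higher baseline rolipram binding tended to show decreased rolipram binding after SSRI". Both statements concern patients with major depression treated with an SSRI.

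Section 10b calls the study exploratory and says that a realistic power calculation cannot be done. It then gives one: a directional hypothesis "for whichever one-sided test is appropriate", and group sizes from "Assuming a 20% dropout from 10 subjects (thus, eight subjects per group").

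**The concern.** Group-matching brings the two age distributions together. It does not remove the variation in V_T that goes with age inside each group. An unpaired test counts that variation as noise, even though age is known for every participant and is the factor on which controls are chosen. The test then assigns the group difference a larger standard error than the matched design gives it.

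With 8 to 10 brain scans per group, each needing an arterial line and a radiation dose, precision that costs no extra scan is worth having. What is at stake is the width of the interval for the MAS-control difference and the chance of detecting a true increase. This is a question of precision; it does not depend on the groups being unbalanced in age or gender.

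**Working it through.** **Inputs.** From section 10b: 8 per group after dropout, or 10 without it; "the coefficient of variation (SD/mean) of VT was 19" per cent; a 19% increase. The standardised difference is d = 19/19 = 1. The test is one-sided. Assumed, because the protocol does not state them: alpha 0.05; within-group age-V_T correlation ρ, shown over a range; a common linear age slope in both groups.

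**1. The plan's own figure.** Section 10b says that this design "will provide a power of 0.80 to detect a 19% increase". For an unpaired t test, ncp = d·√(n/2) and df = 2n − 2.
- n = 8: ncp = 2.00, df 14, critical value 1.761, power 0.601.
- n = 10: ncp = 2.24, df 18, critical value 1.734, power 0.694.

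The stated 0.80 does not reproduce for two independent groups of 8. The gains below are measured from about 0.60 and 0.69.

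**2. Formula for the adjusted test.** With equal mean ages, age in the model multiplies the residual variance by 1 − ρ² and costs one degree of freedom: ncp = √(n/2)/√(1 − ρ²), df = 2n − 3. At ρ = 0.5 the variance falls by 25% and the standard error by 1 − √0.75 = 13%.
- n = 8: power 0.599 (ρ 0), 0.633 (0.3), 0.706 (0.5).
- n = 10: power 0.692, 0.727, 0.797.

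At ρ = 0.5 these are gains of 10.5 and 10.4 points. That is somewhat too favourable: it sets an unmatched baseline against a perfectly matched adjusted test.

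**3. Simulation of both tests on the same data** (100,000 trials per setting). Perfect matching gives each control the age of a patient; chance balance draws ages independently. Group-matching should lie between the two.

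| n per group | ρ | Perfect matching: unadjusted → adjusted | Chance balance: unadjusted → adjusted |
|---|---|---|---|
| 8 | 0 | 0.603 → 0.600 (−0.3) | 0.603 → 0.575 (−2.8) |
| 8 | 0.2 | 0.605 → 0.616 (+1.1) | 0.603 → 0.588 (−1.5) |
| 8 | 0.3 | 0.608 → 0.635 (+2.7) | 0.599 → 0.605 (+0.6) |
| 8 | 0.5 | 0.616 → 0.705 (+8.9) | 0.602 → 0.679 (+7.7) |
| 10 | 0 | 0.695 → 0.693 (−0.2) | 0.695 → 0.671 (−2.4) |
| 10 | 0.2 | 0.696 → 0.706 (+1.0) | 0.695 → 0.687 (−0.8) |
| 10 | 0.3 | 0.700 → 0.725 (+2.5) | 0.696 → 0.706 (+1.0) |
| 10 | 0.5 | 0.718 → 0.798 (+8.0) | 0.693 → 0.776 (+8.3) |

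**4. Why chance imbalance costs power.** Estimating the age slope inflates the variance of the adjusted difference by 1 + 1/(2n − 4) on average: 1.083 at n = 8 and 1.063 at n = 10. Adjustment breaks even when 1 − ρ² offsets this, at ρ = √(1 − 1/1.083) ≈ 0.28 for n = 8 and √(1 − 1/1.063) ≈ 0.24 for n = 10.

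**5. Type I error of the unadjusted test.** With perfect matching at ρ = 0.5, the true standard error is √0.75 = 0.866 of the one the test assumes. The effective cut-off at n = 8 is 1.761/0.866 = 2.03, with a tail area of about 0.031 on 14 df. Simulation gives 0.031 at both sizes, against 0.050 for the adjusted test. At ρ = 0.3 the unadjusted figure is about 0.042 to 0.043. With chance balance both tests hold 0.05.

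**The case against.** The strongest objection is that the size of the gain rests on a correlation that the protocol never gives. At ρ below about 0.25 to 0.3, if mean ages are balanced only by chance, the adjusted model loses power. Balance in the brain-scan groups is not assured either, since participants choose which scans to have (section 4d). All of this stands, and it is why the result is a range. Two further assumptions also stand as limits: the 19% CV comes from healthy subjects whose age spread is not given, and a common linear age slope is uncertain in a mosaic disease with 8 to 10 patients.

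A reader might infer from the Introduction that the sponsor has shown V_T to depend on age, or that this plan departs from its own practice. The documents do not support that. The covariate analysis was of within-patient change in binding after SSRI treatment in depression, and the remark on young patients has the same setting. The closer precedent, the comparison of V_T between depressed patients and controls, describes age and gender matching and mentions no covariate. The precedent is only indirect support.

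It is also said that the plan is exploratory and that its wording leaves the test open. That limits the severity, but it does not supply an adjusted analysis. V_T is still the named primary outcome with a directional hypothesis, and an open choice is a reason to settle the model beforehand.

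**Conclusion.** The point holds as a moderate, inexpensive improvement in precision. Age is a matching factor, no covariate is specified, and any age-related V_T variance stays in the error term. Under one-sided 5%, d = 1 and 8 to 10 per group, adjustment changes power by about −3 to 0 points at ρ = 0, +1 to +3 at 0.3, and +8 to +9 at 0.5.

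Two stronger readings should be resisted. First, the unadjusted test is not invalid: after matching it errs on the conservative side, and nothing here shows bias. Second, age adjustment does not rescue the power claim: at 8 per group and ρ = 0.5, adjusted power is at most about 0.71, still short of 0.80. That shortfall needs its own correction.

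**What to change.** In section 10a, before the group comparison is run:

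- First estimate the age-V_T correlation in the sponsor's existing healthy-control rolipram scans and record it. A value well below 0.3 would leave little power argument for the change.
- Make a linear model of brain V_T on group and continuous age the primary analysis, and report the adjusted MAS-control difference with its confidence interval.
- Keep the t or Mann-Whitney test as a sensitivity analysis.
- State the alpha.

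The cost is a few lines of text, one residual degree of freedom, a linearity assumption for age, and up to about 3 power points if age is unrelated to V_T and mean ages differ by chance. No extra scans or data are needed.

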Outcome measures: The primary outcome measure will be obtained in brain scans as the amount of radioligand binding quantified as distribution volume ($V_{\rm T}$). Calculated from both brain and plasma data, $V_{\rm T}$ reflects rolipram binding to PDE4, corrected for any individual differences in metabolism of the radioligand or regional blood flow in brain. The secondary outcome measure will be obtained in whole body scans as area under the curve (AUC) of radioactivity expressed as standard uptake value (SUV). SUV is calculated by normalizing radioactivity in PET images to injection activity and body weight. $V_{\rm T}$ in brain will be compared between subjects with MAS and healthy controls. AUC will be compared within-subjects with MAS between areas of craniofacial fibrous dysplasia and adjacent unaffected bone. AUC of whole body scans will also be compared between subjects with MAS and healthy controls. We hypothesize that subjects with MAS will show greater rolipram binding than healthy controls in brain regions, as well as greater rolipram uptake in bones affected by fibrous dysplasia than in unaffected bones. The third outcome measure will be the difference in SUV between the baseline whole body scan and the blocked (after roflumilast) whole body scan. This will help determine the amount of specific $[^{11}C](R)$ -rolipram binding in the periphery. We hypothesize that the $[^{11}C](R)$ -rolipram signal in the blocked scan will be greatly reduced, indicating that a majority of the signal in the baseline scan is specific

Table of Contents

1.	Introduction	6
2.	Study Objectives	10
3.	Subjects	11
4.	Study Design and Methods	12
5.	Management of Data and Samples	16
6.	Additional Considerations	17
7.	Risks and Discomforts	17
8.	Subject Safety Monitoring	19
9.	Outcome Measures	20
10.	Statistical Analysis	21
11.	Human Subjects Protection	21
12.	Anticipated Benefit	24
13.	Classification of Risk	24
14.	Consent Documents and Process	24
15.	Data and Safety Monitoring	25
16.	Quality Assurance	25
17.	Reporting of Unanticipated Problems, Adverse Events and Protocol Deviations	26
18.	Alternatives to Participation	26
19.	Privacy	26
20.	Confidentiality	26
21.	Conflict of Interest	27
22.	Technology Transfer	27
23.	Research and Travel Compensation	27
24.	References	29
25.	Attachments/ Appendices	31

List of Abbreviations

AUC	area under the curve
cAMP	3', 5'-cyclic adenosine monophosphate
MAS	McCune-Albright syndrome
MDD	major depressive disorder

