The purpose of this study is to assess whether uptake in dysplastic bone reflects parent radioligand binding to the enzyme or merely accumulation of radiometabolites, which are expected to have no affinity for the enzyme. For this purpose, we need not administer a receptor saturating dose of roflumilast, as the Lassen occupancy plot has great sensitivity to measure the percentage occupancy and then to extrapolate to 100% occupancy (Cunningham et al., *J. Cereb. Blood Flow & Metab.*, 30: 46-50, 2010). The sensitivity derives from the fact that it is a within subject comparison of multiple regions (in brain or periphery) at baseline and after blockade. We have used the Lassen plot numerous times, including to measure the occupancy of PDE4D subtype by the therapeutic candidate BPN14470. The figure below shows that that the occupancy (i.e., slope) is ~65% and the nondisplaceable uptake (V_{ND} or x-intercept) is ~4.9 mL \cdot cm⁻³.

2. Study Objectives

This study will investigate cAMP signaling in the brains of individuals with MAS using $[^{11}C](R)$ -rolipram PET imaging.

a. Primary objectives

We will study PDE4 levels in patients with MAS by comparing $[^{11}C](R)$ -rolipram binding in various brain regions between patients and age-matched healthy controls. In addition, in whole body imaging of patients with MAS, we will compare $[^{11}C](R)$ rolipram uptake between areas of fibrous dysplasia and adjacent unaffected bones. In whole body scans, we will also compare $[^{11}C](R)$ -rolipram uptake in peripheral organs between subjects with MAS and healthy controls. The reason for doing the latter comparison is that some tissues of MAS may contain the *GNAS* mutations even if there are no obvious structural changes.

b. Secondary objective

In order to quantify the amount of $[^{11}C](R)$ -rolipram binding in patient whole body scans, we will perform a blocking scan with 500 µg roflumilast, a FDA approved PDE4 inhibitor. Because of potential differences in metabolism of $[^{11}C](R)$ -rolipram in in the periphery of healthy controls and patients, it is difficult to interpret whether or not the $[^{11}C](R)$ -rolipram uptake is specific. By performing a blocking scan, we can quantify the amount of specific $[^{11}C](R)$ -rolipram binding to determine if there is a difference between healthy controls and patients.

3. Subjects

a. Description of study populations

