All subjects, including those who receive only a whole body scan, will undergo a dedicated MRI of the brain for co-registration of PET images for analysis and to estimate brain morphology. Portions of the whole body PET scans image the brain. However, both volunteers and patients need not repeat the MRI scan if they had one of appropriate sequence within the prior year.

The MRI will be performed on a 3 Tesla magnet without the use of gadolinium contrast. Subjects will undergo safety screening prior to the MRI to rule out contraindications. The MRI will take place at the NIH Clinical Center and requires about

thirty to forty minutes. If subjects become anxious during a scan, lorazepam (0.5–1 mg) or another benzodiazepine may be administered orally, if not clinically contraindicated. Subjects can also request that the operator stop the scan at any time. Women of childbearing potential without a history of sterilization will be tested for pregnancy with a urine test prior to the MRI.

If the scan is cancelled or incomplete due to a problem with the scanner, the scan will be repeated on the same or on another day if the participant is willing.

v. Neuropsychiatric testing

Subjects with MAS will have the following examinations:

- 1. Wechsler Adult Intelligence Scale, Fourth Edition (WAIS-IV) or the Kaufman Brief Intelligence Test, Second Edition (KBIT-2) (17, 18)
- 2. Structured Clinical Interview for Non-Patient (SCID-NP) or SCID Patient Edition (SCID-P)
- 3. Edinburgh Handedness Inventory

Both the WAIS-IV and KBIT-2 provide an overall assessment of intelligence. SCID-NP characterizes neuropsychiatric symptoms. The Edinburgh Handedness Inventory assesses the dominance of a person's right or left hand. A decision to perform either the SCID-NP or SCID-P will be based on the patient's psychiatric history.

The WAIS-IV, KBIT-2, or the Edinburgh Handedness Inventory will not be repeated if the subject has already undergone these assessments under protocol 98-D-0145. The SCID-NP (or SCID-P) will not be repeated if performed within the past month.

e. End of participation

Study participation will end with the last PET or MRI scan the participant agreed to do. Patients will return for follow up under 98-D-0145. No follow up care will be needed for healthy volunteers.

5. Management of Data and Samples

a. Storage

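### Section 10a does not carry the lesion-versus-adjacent-bone comparison set out in the précis and objectives, and gives no within-patient test for bone lesions whose opposite side is affected or unavailable

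*Combined protocol and SAP*

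**What the plan says.** The précis, under Outcome measures, fixes measure, contrast and design: "AUC will be compared within-subjects with MAS between areas of craniofacial fibrous dysplasia and adjacent unaffected bone". It then adds a second comparison: "AUC of whole body scans will also be compared between subjects with MAS and healthy controls". Section 2a, Primary objectives, repeats the lesion contrast as "uptake between areas of fibrous dysplasia and adjacent unaffected bones" and again lists patients against healthy controls separately. It gives that comparison its own reason: "The reason for doing the latter comparison is that some tissues of MAS may contain the" *GNAS* mutations without any obvious structural change.

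Section 10a gives a different rule for peripheral organs in MAS: "for comparisons of PET data between affected and unaffected organs, a paired test will be applied if the contralateral side is unaffected". Otherwise, "If contralateral side is also affected or not available, an unpaired test will be applied to compare the same tissue/organ between patients and healthy controls". Adjacent bone is not mentioned. Section 10b names bone as an example of a peripheral organ, so the rule covers bone lesions.

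Section 3b requires every MAS participant to "Have craniofacial fibrous dysplasia". Section 4d(iv) notes: "Portions of the whole body PET scans image the brain". Section 9b makes AUC of SUV the secondary outcome. It warns that group comparisons of AUC may be in error if clearance differs markedly between groups, and it plans venous sampling to correct for this.

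**The concern.** The reference region and the fallback in section 10a both differ from those in the précis and objectives. Adjacent bone and contralateral bone are different regions. When the contralateral side cannot serve, section 10a moves from a contrast within one patient to a contrast between patients and other people, although the adjacent bone named in the précis may be visible on the same image. An analyst following section 10a would then answer a different question for those lesions.

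The fallback also loses the main advantage of the within-patient contrast. SUV already adjusts for injected activity and body weight, but two regions in one patient also share the same plasma input. Patients and controls do not, and this is the weakness that section 9b describes. Lesions would moreover be sorted between two tests by the state of the opposite side, and section 10a does not say how the two results are to be read together.

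**Working it through.** The point rests on the text. The plan states no figure for the lesion comparison, so there is none to reproduce.

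**1. The passages side by side**

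| Place | Reference for the lesion | Design | Role of patient-versus-control |
|---|---|---|---|
| Précis | Adjacent unaffected bone | Within-subject | Additional |
| Section 2a | Adjacent unaffected bones | In patients with MAS | Additional, with its own reason |
| Section 10a, opposite side unaffected | Contralateral side | Paired | Separate group comparison |
| Section 10a, opposite side affected or unavailable | Same tissue in healthy controls | Unpaired | Takes the place of the paired test |

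In the last row, section 10a supplies no within-patient test. Reading bone out of the word organs does not help: section 10b counts bone as a peripheral organ, and if bone were excluded, section 10a would contain no lesion analysis at all.

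**2. Illustration: power**

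Assumptions: true difference of 1 SD, one-sided alpha 0.05, t-tests. Eight patients and eight controls follow section 10b (10 per group less 20%). Twelve controls is the completion target in section 3a. The within-patient correlation rho is not in the documents.

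- Paired: dz = 1/√(2(1 − rho)); noncentrality = dz·√n; df = n − 1. Example: rho 0.5 gives dz = 1, and n = 8 gives noncentrality 2.83 and power 0.82.
- Unpaired: noncentrality = √(ab/(a + b)); df = a + b − 2. Example: 8 v 8 gives noncentrality 2.00 and power 0.60.

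| rho | Paired n = 8 | Paired n = 4 |
|---|---|---|
| 0 | 0.56 | 0.30 |
| 0.25 | 0.67 | 0.36 |
| 0.5 | 0.82 | 0.46 |
| 0.75 | 0.97 | 0.69 |

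Unpaired power is 0.45 for 4 v 8, 0.60 for 8 v 8 and 0.68 for 8 v 12. Pairing therefore gains power clearly only at moderate or high rho; at rho 0 it is slightly worse than 8 v 8. At rho 0.5 the 4 v 8 fallback (0.45) matches a paired test on four patients (0.46). In that case the loss comes from splitting the sample, not from the fallback test itself.

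**3. Illustration: group difference in plasma exposure**

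Assumptions: no true tissue difference, tissue AUC proportional to plasma exposure, the difference left uncorrected, and a CV of 19% to 30%. The 19% is the brain V_T figure in section 10b, borrowed for bone. Standardised shift d = shift/CV; for example 0.10/0.19 = 0.53. Noncentrality = d·√(ab/(a + b)). Rejection rates at nominal one-sided 5%, for CV 30% to CV 19%:

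| Patients' exposure | 4 v 8 | 8 v 8 |
|---|---|---|
| 5% higher | 8% to 11% | 9% to 13% |
| 10% higher | 13% to 20% | 16% to 26% |
| 10% lower | 1.6% to 0.7% | 1.1% to 0.4% |

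A paired test stays at 5% under these assumptions because both regions are scaled by the same factor. That is a consequence of the assumption, not evidence about real lesion and reference bone.

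**The case against.** The strongest reply is that this is a combined protocol and SAP, and that the précis itself states the within-subject contrast with adjacent bone. Section 10a does not withdraw it. Its contralateral rule can be read as the choice of test for organs that have a natural counterpart. On that reading, section 10a omits an analysis and does not replace one. This stands as a possible reading, so a reader should not infer that the plan has abandoned the within-patient comparison. It does not remove the need to reconcile the text, because the only stated rule for choosing between paired and unpaired tests would still send some bone lesions to a between-group test.

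Contralateral bone is also a defensible reference. Adjacent bone may receive spill-over from the lesion, or carry the mutation without visible change, as section 2a allows. Either would bias towards no difference. This supports keeping contralateral bone as a further comparison, but not dropping the within-patient test when that side is unusable.

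Third, section 9b plans venous sampling to correct for clearance. That is fair, although section 10a does not say how the correction enters the AUC comparison.

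Finally, it is an inference that usable adjacent bone will be on the scan. The entry criterion and the partial head coverage make it plausible; the documents do not say how often it will be so.

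**Conclusion.** The inconsistency is real and should be corrected. For bone lesions with an affected or unavailable contralateral side, section 10a provides no within-patient test, although the précis and objectives call for lesion against adjacent bone and treat patient-versus-control as an addition.

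Its reach is modest. The comparison is listed under primary objectives, but its measure is a secondary outcome of a study that describes itself as exploratory, and the brain V_T analysis is unaffected. The number of patients diverted is not given; if it is small, little is lost.

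A reader might infer that the fallback costs a definite amount of power or produces a known excess of false positives. The documents support neither. The power advantage of pairing depends on an unstated correlation, and the false-positive rates depend on an assumed, uncorrected exposure difference and a CV borrowed from brain. Nor is the fallback invalid in itself: it compares lesion bone with the unaffected bone of other people, which is a legitimate but different question. The finding concerns bone only; for other paired organs a contralateral reference is natural.

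**What to change.** In section 10a, for bone lesions, state that AUC of SUV in craniofacial fibrous dysplasia will be compared with adjacent unaffected bone in the same patient by a paired test. State that the adjacent region will be chosen before uptake values are read. Add that the patient-versus-control comparison of bone is a separate analysis that does not replace the paired test. Unaffected contralateral bone may be kept as a further paired comparison, and the existing rule for other organs can stay.

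If the sponsor prefers contralateral bone as the lead reference, align the précis and section 2a with section 10a, but still keep a within-patient test where adjacent unaffected bone is available.

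Averaging over lesions, pooling the two reference types and sensitivity analyses are optional; the inconsistency does not require them.

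The cost is wording and some extra region drawing on scans already planned, with no new scans or blood samples. The downside is the possible bias of adjacent bone towards no difference, which is a reason to retain the patient-versus-control comparison alongside. Some patients may have no usable reference bone.
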